**d. Power analysis**

In alignment with the advice of the funding institute (NCCIH) and intended purpose of pilot feasibility trials, we did not conduct a power analysis for this trial. Rather, we selected a sample size (N=40) based on pragmatics, the needs of the trial, and our team's previous pilot studies, that will provide an accurate indication of the feasibility of the research procedures.

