**It is feasible to deliver MBCT via e-health technologies.** E-health mindfulness interventions are feasible and can improve health outcomes in patients with medical problems. However, research has focused on websites that patients use independently, which does not allow for synchronous contact with a clinician or peers, leading to a smaller treatment effect and increased attrition, and eliminating the health benefits of social support. Group videoconferencing combines accessibility with synchronous contact, shows comparable efficacy with in-person treatments, and is a validated approach to behavioral intervention delivery. Two studies demonstrated the feasibility of videoconferencing to deliver mindfulness interventions to patients at their own home. Thus, group videoconferencing is a promising but underutilized approach to MBCT delivery.

**MBCT via group videoconferencing is likely to be attractive and feasible for ACS patients.** Web-based mindfulness interventions are feasible and reduce depression symptoms in patients with cardiovascular disease and other older adult populations. The AHA has emphasized that a benefit of meditation for cardiac health is the possibility of online delivery, but no research has applied MBCT via group videoconferencing to ACS patients with elevated depression symptoms.

**Our preliminary work supports the use of virtual MBCT for ACS patients.** We recently conducted a qualitative study (individual patient interviews) to solicit patient's perspectives and needs for a behavioral depression treatment based on MBCT (IRB Protocol Number 2018P001000). Patients were open and interested in a mindfulness program, identified a range of symptoms and needs for the intervention to target, offered suggestions for promoting videoconferencing feasibility, and expressed openness to participate in dried blood spot research procedures. We developed an adapted MBCT protocol based on this feedback, which we recently tested in an open pilot trial of n=7 patients with ACS and depressive symptoms (IRB Protocol Number 2020P000045). Those who completed the intervention (n=4) reported high ratings of intervention acceptability, videoconference acceptability, comfort with the dried blood spot procedures, and improvements in depression and anxiety symptoms.

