## II. SPECIFIC AIMS

- a. Aim 1:** To establish, in a pilot RCT (approx. N=50 participants) with a time- and attention-matched health enhancement control, (a) the feasibility of the recruitment procedures (screening, eligibility, enrollment rates), and feasibility and acceptability of the (b) MBCT and control interventions (adherence, retention, fidelity, satisfaction, group videoconferencing delivery) and (c) data collection procedures by group (adherence, satisfaction). Hypothesis 1a: Recruitment will be feasible as evidenced by screening, eligibility, and enrollment rates; (1b) the MBCT and control interventions and (1c) data collection procedures in both groups will be feasible and acceptable.
- b. Aim 2 (exploratory):** To explore within-group changes in psychosocial and physical health outcomes following virtual MBCT and the control intervention (e.g., depression, inflammation, emotion regulation, pro-sociality, and health behaviors).

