#### **IV. SUBJECT ENROLLMENT**

**a. Methods of enrollment, including procedures for patient registration and or randomization**

Study staff will approach patients about participating in the study using one the modalities discussed in section III.b. For patients who are not interested in participation, study staff will discontinue contact. For patients who are interested in participation, study staff will screen patients for eligibility (criteria detailed in section III.a). If a patient screens as eligible, they will be asked to provide informed consent using one of the procedures detailed in section IV.b. Following informed consent patients will be 1:1 randomized (see section IV.c) and enrolled in the study using a random number generator.

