## VI. BIOSTATISTICAL ANALYSIS

### a. Specific data variables being collected for the study

The primary outcomes are feasibility and acceptability of the intervention and research procedures (Table 1). Study staff will record all feasibility outcomes throughout recruitment, screening, enrollment, and the intervention, data collection, and follow-up phases.

Table 1. PRIMARY OUTCOMES	
Feasibility	
Recruitment	$\geq 70\%$ consent to screening; $\geq 70\%$ meet screening criteria; $\geq 70\%$ of eligible enroll; enroll $\geq 20$ participants/month
Eligibility criteria	$< 20\%$ ineligible due to each criterion; reasons for ineligibility; reasons for refusal; characteristics of refusers
MBCT and control interventions	Adherence: $\geq 75\%$ session attendance; retention: $\geq 75\%$ post-assessments, $\geq 70\%$ follow-up assessments completed; fidelity: checklist score $\geq 80\%$ ; $\geq 75\%$ complete home practice at least 3 days/week
Videoconferencing	$< 20\%$ of connections dropped during session; $< 20\%$ of sessions missed due to technical problems; number ( $M < 2.0$ ) and type of problems; $< 20\%$ ask for extra training, type of extra training needed
Blood spots	Adherence: $\geq 75\%$ submitted at baseline, post-intervention, $\geq 60\%$ submitted at follow-up; 80% adequate quality
Acceptability	
MBCT and control interventions	Session satisfaction and helpfulness, enjoyment, relevance, utility of each session component (1=not at all, 10=very much; $M \geq 7.5$ ; post-session survey ); overall program satisfaction ( $M \geq 7.5$ ), $\geq 75\%$ plan to use the skills, $\geq 75\%$ would recommend the program to others ( post-intervention )

	survey); likes, dislikes, suggestions for improvement (exit interview); <math>\geq 60\%</math> continue meditation practice (follow-up survey)
Videoconferencing	Ease and confidence of use (1=not at all, 10=extremely <math>M \geq 7.5</math>), interference of technical problems (1=none, 10=extreme; <math>M < 2.0</math>), audiovisual quality and overall satisfaction (1=poor, 10=excellent; <math>M > 7.5</math>; post-session survey); pros and cons, suggestions for improvement (exit interview)

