### **c. Statistical methods**

**Aim 1.** I will calculate frequencies and proportions to assess feasibility outcomes, and means and standard deviations or medians and interquartile ranges to assess acceptability ratings. T-tests or chi-square tests will be used to compare eligible patients who did and did not enroll in terms of demographic and clinical variables, and feasibility and acceptability across enrolled patients based on gender, and medical/psychiatric factors. I will use independent samples t-tests to compare adherent and non-adherent participants from each group on baseline depression and clinical and demographic variables. Exit interviews will be audio recorded, transcribed, and iteratively analyzed using thematic content analysis. Approximately 2-3 members of the study team will review the transcripts to identify common themes and develop a coding framework. We will review our results for agreement and comparison to the raw data, and resolve discrepancies

through discussion with [name] until. All transcripts will be coded according to the coding framework.

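### The planned sample size is given as about 50 in Aim 1 and as 40 in the Power analysis section, and nothing in the plan reconciles the two.

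*Combined protocol and SAP*

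**What the plan says.** Two sections of the combined protocol and SAP give a planned size for this trial.

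- Section II, Aim 1, sets out to establish feasibility "in a pilot RCT (approx. N=50 participants"), against a matched control.
- Section VI.d explains that no power analysis was done, in line with the funder's advice for pilots, and continues: "we selected a sample size (N=40) based on pragmatics, the needs of the trial". It adds the team's previous pilot studies as a further basis and says that this number will indicate feasibility accurately.

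Three other places bear on what the number might count.

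- Section IV.a makes randomisation and enrolment one step: "Following informed consent patients will be 1:1 randomized (see section IV.c) and enrolled in the study". Section IV.c repeats the 1:1 ratio.
- Table 1 in section VI.a sets the retention benchmarks: "retention: $\geq 75\%$ post-assessments, $\geq 70\%$ follow-up assessments completed". These are success criteria; no section uses them to set N.
- Section VI.c, Aim 1, plans a descriptive analysis: "I will calculate frequencies and proportions to assess feasibility outcomes".

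Neither statement of N says whether it refers to randomised or completing participants, and no expected completion rate is given anywhere.

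**The concern.** The number to enrol is a basic design parameter, and the plan gives it two values. Aim 1 marks its figure as approximate, but 40 is 20% below 50, which is more than that qualifier can reasonably cover. Section VI.d has no such qualifier and reports a number already chosen. At least one of the two statements therefore needs correcting or explaining.

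At stake are the clarity of the enrolment target, the arm sizes, and the number of participants who will contribute outcome data. A final report on 40 participants could say that the planned size was reached, citing section VI.d, or that it was missed by 10, citing Aim 1. Recruitment is part of the primary feasibility outcome, so that ambiguity is worth closing.

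**Working it through.** **Can either figure be reproduced?** No. The plan gives no power, effect size, standard deviation, precision target or dropout rate from which 40 or 50 would follow. The check is therefore one of consistency.

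**Inputs.** N = 50, approximate (section II, Aim 1); N = 40 (section VI.d); 1:1 allocation (sections IV.a and IV.c); minimum retention of 75% post-intervention and 70% at follow-up (Table 1).

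**Size of the gap.**
- 50 − 40 = 10 participants; 10/40 = 25% and 10/50 = 20%.
- Per arm, assuming equal arms: 40/2 = 20 and 50/2 = 25.

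**Participants with data at the minimum benchmarks, pooled over arms (N × retention).**

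| Randomised | Post-intervention | Follow-up |
|---|---|---|
| 40 | 0.75 × 40 = 30 | 0.70 × 40 = 28 |
| 50 | 0.75 × 50 = 37.5, so 38 | 0.70 × 50 = 35 |

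If the minimum must be met in each arm separately, the follow-up count for N = 50 becomes 36: 0.70 × 25 = 17.5, so 18 per arm. The other three totals do not change.

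**Can 50 and 40 be randomised and completing participants?**
- Completion needed: 40/50 = 80%, a loss of 20%.
- This lies above both retention minimums, so it is compatible with Table 1.
- It does not follow from Table 1. At exactly the benchmark rates, 40 completers would need 40/0.75 = 53.3, so 54 randomised, or 40/0.70 = 57.1, so 58 randomised.

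**Precision, for the optional wording only.** These are 95% Wilson intervals at the smallest count that reaches 75%, with participants treated as independent.

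| Basis | N = 40 | N = 50 |
|---|---|---|
| One arm | 15/20 (75%): 53–89% | 19/25 (76%): 57–89% |
| Pooled | 30/40 (75%): 60–86% | 38/50 (76%): 63–86% |

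The pooled width is 26 points at N = 40 (59.8 to 85.8) and 23 at N = 50 (62.6 to 85.7). Precision alone does not show which figure was intended.

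**The case against.** The strongest reply is that this is a feasibility pilot with no powered hypothesis. Every percentage benchmark in Table 1 is calculated on the participants who enrol, none refers to a total N, and precision hardly differs between 40 and 50. A reader can also reconcile the figures by assuming 20% loss. Most of this stands, and it limits the consequence. It does not remove the contradiction, because the reader has to supply the assumption.

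Several stronger readings are tempting, and the documents do not support them.

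- *The missing dropout allowance is a defect in itself.* A pilot without a powered target has no required number of completers to inflate towards, and retention is one of the outcomes under study. An allowance matters here only because it could have linked 50 to 40.
- *The team inflated 40 wrongly.* Multiplying 40 by 1.25 gives 50, whereas dividing by 0.75 gives 54. Nothing in the plan shows that any inflation was done.
- *The team's own pilot rules out 80% completion.* Section I.b reports an "open pilot trial of n=7 patients with ACS and depressive symptoms", of whom 4 completed the intervention. That is 57%, with a 95% Wilson interval of 25–84%, which includes 80%. It also concerns completing the intervention in a single-arm study, not completing assessments in this trial.
- *The Table 1 benchmarks lose their denominators.* They do not; the percentages apply to whatever number enrols.
- *Descriptive proportions without intervals, or the claim of accuracy in section VI.d, are errors.* Descriptive analysis is a legitimate choice in a pilot. The claim is loosely worded, which is a separate and optional matter.

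**Conclusion.** The point holds as an internal inconsistency: about 50 in Aim 1, 40 in section VI.d, and no statement connecting them. The gap is 10 participants, 5 per arm. At minimum retention on the pooled total it amounts to about 8 participants with post-intervention data (38 − 30) and 7 with follow-up data (35 − 28). No planned analysis or decision rule fails, so the consequence is modest, but a core design number should not have two values and the correction costs almost nothing.

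The conclusion that the figures conflict rests only on the two passages. The counts with data assume equal arms and retention exactly at the Table 1 minimums. The documents do not show which figure is intended or what either one counts, and this point takes no position on that.

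**What to change.** State one planned N in both section II (Aim 1) and section VI.d, give the number per arm, and say whether it counts randomised or completing participants. If 50 and 40 are meant as randomised and completing, state both figures in both places, together with the 80% completion that links them.

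Optional, and not part of the error: if section VI.d keeps a claim about accuracy, replace it with the precision of the chosen N. Give it by arm as well as pooled, since Aim 1 states its feasibility hypothesis for both interventions and for data collection in both groups. Examples by arm are 15/20 with a 95% Wilson interval of 53–89%, or 19/25 with 57–89%. Add that group delivery could widen these intervals.

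The cost is about one sentence in each of the two sections, plus one or two more for the optional part. It needs no redesign and no participants beyond the number that the team already intends. A stated interval will look less favourable than the present wording.

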**c. Treatment assignment and randomization**

Participants will be randomized to a MBCT or a time- and attention-matched health enhancement control in a 1:1 design using a random number generator.

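### The claim that N=40 gives an accurate picture of feasibility has no precision figure behind it, and participant-level benchmarks near 75% are judged on point estimates too imprecise to class true rates within about 10 points of the cut-off

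*Combined protocol and SAP*

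**What the plan says.** Section VI.d says "we did not conduct a power analysis for this trial" and explains that "we selected a sample size (N=40) based on pragmatics, the needs of the trial, and our team's previous pilot studies". It then credits that size with a property: it is one "that will provide an accurate indication of the feasibility of the research procedures". No margin, interval width or error rate accompanies the statement. Section II describes the trial differently, as Aim 1 is to be met "in a pilot RCT (approx. N=50 participants".

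Feasibility and acceptability are the primary outcomes (VI.a, VI.b). Table 1 gives them numerical benchmarks. Examples are at least 75% of post-intervention assessments completed, at least 70% at follow-up, at least 75% of blood spots submitted at baseline and post-intervention, and mean programme satisfaction of at least 7.5 on a 1 to 10 scale.

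For the analysis, VI.c (Aim 1) says "I will calculate frequencies and proportions to assess feasibility outcomes", with means and SDs or medians and interquartile ranges for ratings. No confidence interval is planned for any benchmark.

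Allocation is "in a 1:1 design using a random number generator" (IV.c). Hypothesis 1c is that "data collection procedures in both groups will be feasible and acceptable", and 1b likewise covers both interventions. Table 1 does not say whether each benchmark is read per arm or on the pooled sample.

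**The concern.** Doing no power analysis is acceptable in a feasibility pilot and is not the complaint. The complaint is that the plan makes a statement about precision, does not quantify it, and then plans an analysis that never displays the uncertainty. Under 1:1 allocation, N=40 means about 20 per arm. At that size, a result that just meets 75% is compatible with true rates well below and well above it.

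The stake is how the primary outcome is reported. Section VIII.b says the results will establish feasibility and guide refinement before a later efficacy trial. As written, 15 of 20 could be reported as meeting the benchmark, on a sample described as accurate, with no sign that a true rate near 51% is not excluded. Equally, a procedure that works well enough could be marked as falling short by chance.

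**Working it through.** **Reproducing N.** This cannot be done. The documents give no margin, power or interval width from which 40 would follow. The check is therefore what 40 (or about 50) delivers.

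**Inputs.** N=40 (VI.d) or about 50 (II); 1:1 allocation (IV.c), so 20 or 25 per arm; benchmark 75% (Table 1, for example post-intervention assessments and blood spot submission). The true rates below are assumptions, shown as a range. Participants are treated as independent, with full denominators.

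**Step 1: exact 95% interval when the benchmark is just met.** For x of n, the Clopper-Pearson limits are the 0.025 quantile of Beta(x, n−x+1) and the 0.975 quantile of Beta(x+1, n−x). The smallest count reaching 75% is 15 of 20, 19 of 25, 30 of 40 or 38 of 50.

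| Observed | Setting | Exact 95% CI |
|---|---|---|
| 15/20 (75%) | per arm, N=40 | 50.9% to 91.3% |
| 19/25 (76%) | per arm, N=50 | 54.9% to 90.6% |
| 30/40 (75%) | pooled, N=40 | 58.8% to 87.3% |
| 38/50 (76%) | pooled, N=50 | 61.8% to 86.9% |

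The most favourable case is still 86.9 − 61.8 = 25.1 points wide. The other benchmarks behave alike at n=20: 14/20 (70%) gives 46% to 88%, and 12/20 (60%) gives 36% to 81%.

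**Step 2: chance that the observed proportion meets 75%.** This is P(X ≥ c), with X binomial(n, p) and c the count above.

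| True rate p | n=20, c=15 | n=25, c=19 | n=40, c=30 | n=50, c=38 |
|---|---|---|---|---|
| 50% | 2.1% | 0.7% | 0.1% | 0.0% |
| 60% | 12.6% | 7.4% | 3.5% | 1.3% |
| 65% | 24.5% | 17.3% | 12.1% | 6.6% |
| 70% | 41.6% | 34.1% | 30.9% | 22.3% |
| 75% | 61.7% | 56.1% | 58.4% | 51.1% |
| 80% | 80.4% | 78.0% | 83.9% | 81.4% |
| 85% | 93.3% | 93.0% | 97.0% | 97.0% |
| 90% | 98.9% | 99.1% | 99.9% | 99.9% |

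A true 70% meets the benchmark in 42% of trials at n=20 and 31% at n=40. A true 80% misses it in 100 − 80.4 = 20% and 100 − 83.9 = 16%. The uncertain zone is not symmetric. Per arm it reaches about 10 points below the cut-off, where a true 65% still passes 25% of the time. Above the cut-off, and on the pooled sample, it is narrower.

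**Step 3: one-off ratings.** The half-width is t(0.975, n−1) × SD / √n. The documents give no SD, so 2 is assumed, with a range of 1.5 to 2.5. If 75% of 20 respond (n=15), it is 2.145 × 2 / √15 = 1.1 points, with a range of 0.8 to 1.4, around a cut-off of 7.5. This applies to ratings made once, such as overall programme satisfaction, and not to ratings repeated after each session.

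**Step 4: rows that do not rest on 20 or 40.** Recruitment rates are based on patients approached, screened or eligible. If each 70% step were exactly met, 40 enrolled would imply 40/0.7 ≈ 58 eligible, 40/0.49 ≈ 82 screened and 40/0.343 ≈ 117 approached. From 1.96 × √(0.21/n), the half-widths are about 12, 10 and 8 points. These are better, but equally unstated.

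**The case against.** The strongest reply is that the trial does what a pilot of this size can do. Under the 15-of-20 rule a true 50% passes 2% of the time and a true 90% passes 99%, so a procedure that plainly fails is distinguished from one that plainly works. That stands. A reader might infer from the wide intervals that the trial cannot tell a failing procedure from a passing one. The calculation does not support this, because the difficulty is confined to rates near the cut-off.

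A reader might also infer a formal go/no-go rule for the later efficacy trial. None is written. Section VIII.b speaks of informing refinement, and Table 1 and VI.c also call for reasons for refusal, types of problem and thematic analysis of exit interviews. Feasibility is therefore not judged on proportions alone. Nor do the documents require each arm to pass separately. Hypotheses 1b and 1c concern both groups, but no joint rule is stated, so a joint pass probability would rest on a rule the plan does not contain.

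It is also right that a binomial with n=20 does not describe all of Table 1. Screening, eligibility and enrolment precede randomisation and have no arm. Dropped connections, sessions missed for technical reasons, fidelity scores and post-session ratings are counted per connection, session or repeated rating. On pooled reading the error rates are lower, as the table shows.

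Finally, anyone given counts and denominators can compute the intervals later, so nothing is lost irretrievably. That lowers the priority. It does not support the accuracy claim, which fails near the cut-off under every reading of the enrolled sample, including 38 of 50 pooled.

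**Conclusion.** The point holds for participant-level benchmarks near 75%. At 20 per arm the data leave about 40 points of uncertainty around a result that just meets the benchmark (51% to 91%), and about 28 points pooled (59% to 87%). True rates within about 10 points of the cut-off cannot be reliably classed per arm. The accuracy statement in VI.d is therefore unsupported, and VI.c plans nothing that would show this to a reader.

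The conclusion assumes independent participants and complete denominators. Correlation within videoconference groups, or missing data, would widen the intervals. It does not depend on whether N is 40 or about 50. The point concerns reporting and justification. No planned analysis is invalidated, so it should be corrected but is not among the most serious faults a plan can have.

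**What to change.** 1. Reconcile the N of 40 in VI.d with the approximate 50 in Section II. Then replace the accuracy claim in VI.d with the precision that N delivers, per arm and pooled. If 40 is kept, the sentence could read: with 20 per arm, an observed 75% has an exact 95% confidence interval of 51% to 91%; with 40 pooled, 59% to 87%. If 50 is kept, use 19/25 (55% to 91%) and 38/50 (62% to 87%).
2. In VI.c, Aim 1, add exact 95% intervals for participant-level proportions and 95% intervals for means. Give them by arm for post-randomisation rows that exist in both arms, for MBCT only for home practice (V.a gives the logs to that arm alone), and overall for screening, eligibility and enrolment. For session-level rows, use intervals that allow for repeated measures within participant or group. State in Table 1 whether each benchmark is read per arm or pooled.
3. Report each met benchmark together with the lowest rate or mean not excluded, or the highest for benchmarks of the less-than kind.

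The cost is a few sentences in VI.a, VI.c and VI.d and a few lines of code. No participants, visits or procedures are added. The price is that the stated precision will look less favourable than the present wording.
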